6.1. Study Intervention(s) Administered

Treatment Regimens, Double-Blind Treatment Period

LY3372689 Dose (mg)	Regimen
0.75	LY3372689: 0.75 mg dose once daily for up to 124 weeks (minimum of 76 weeks) (Visit 2 [Week 0]–Visit 29 [Week 124]).
3.0 ^a	LY3372689: 3.0 mg dose once daily for up to 124 weeks (minimum of 76 weeks) (Visit 2 [Week 0]–Visit 29 [Week 124]).
Placebo	Placebo dose once daily for up to 124 weeks (minimum of 76 weeks) (Visit 2 [Week 0]–Visit 29 [Week 124]).

^a Dose may be reduced from 3 to 1.5 mg if deemed necessary. Refer to Section 6.6.

Investigational products used in this study are:

- LY3372689, and
- Placebo.

Investigational products are administered orally once daily in the morning at approximately the same time each day. LY3372689 may be taken with or without food. All LY3372689 strengths and placebo will be identical tablets.

This study will utilize a 76-week common close design. Under the common close design, all enrolled participants will remain on double-blind randomized treatment and complete assessments until the last enrolled participant that has not discontinued from treatment has achieved 76 weeks of assigned treatment. The maximum duration of treatment is 124 weeks.

The table below lists the study interventions used in this clinical study.

Intervention Name	LY3372689	Placebo	Flortaucipir F18
Authorized as defined by EU Clinical Trial Regulation	Not authorized	Not authorized	Not authorized

Packaging and Labeling

Study intervention will be supplied by the sponsor or designee in accordance with current Good Manufacturing Practice. Clinical trial materials will be labeled according to the country's regulatory requirements. All IPs will be stored, inventoried, reconciled, and destroyed according to applicable regulations. Clinical trial materials are manufactured in accordance with current Good Manufacturing Practices.

6.2. Preparation/Handling/Storage/Accountability

1. The investigator or designee must confirm appropriate temperature conditions have been maintained during transit for all IP received and any discrepancies are reported and resolved before use of the IP.
2. Only participants enrolled in the study may receive IP, and only authorized site staff or designee may supply or administer IP. All study intervention must be stored in a secure, environmentally controlled, and monitored (manual or automated) area in accordance with the labeled storage conditions with access limited to the investigator and authorized site staff or designee.
3. The investigator, institution, or the head of the medical institution (where applicable) is responsible for IP accountability, reconciliation, and record maintenance (i.e., receipt, reconciliation, and final disposition records).
4. Further guidance and information for the final disposition of unused IP are provided by the sponsor.

6.3. Measures to Minimize Bias: Randomization and Blinding

This is a double-blind study (study periods 2a and 2b), with design to maintain blinding to treatment. To preserve the blinding of the study, a minimal number of Lilly personnel will see the randomization table and treatment assignments before the study is complete.

For between-group comparability, participant randomization will be stratified by the investigative site, tau burden (moderate versus high) as defined by flortaucipir PET, and by prior or current use of any approved disease-modifying therapy for AD. Enrollment of high tau burden participants will be capitated at a predetermined proportion of the total enrolled population. Hence, study eligibility based on flortaucipir PET scan results may change as the study progresses. Assignment to treatment groups will be determined using an interactive web response system (IWRS). The IWRS will be programmed using the dynamic allocation (minimization) method of Pocock and Simon (1975), to balance the treatment arms using three factors: investigative site, tau burden, and prior or current use of any approved disease-modifying therapy for AD. This is to achieve balanced participant assignment between treatment arms as much as possible within each stratum and at the study level. Randomization into 1 stratum may be discontinued at the discretion of the sponsor.

Blinded site personnel will dispense study intervention and confirm that they have located the correct packages by entering a confirmation number found on the label into the IWRS.

The independent external DMC is unblinded to randomization.

If an investigator, site personnel performing assessments, or participant is unblinded, the participant must be discontinued from the study. In cases where there are ethical reasons to have the participant remain in the study, the investigator must obtain specific approval from a Lilly-designated Medical Monitor for the participant to continue in the study.

In case of an emergency, the investigator has the sole responsibility for determining if unblinding of a participant's treatment assignment is warranted for medical management of the event. The participant's safety must always be the first consideration in making such a determination. If a participant's treatment assignment is unblinded, Lilly must be notified immediately. If the

investigator decides that unblinding is warranted, it is the responsibility of the investigator to promptly document the decision and rationale and notify Lilly as soon as possible.

Participants who meet all criteria for enrollment will be assigned a study (participant) number at Visit 601 or Visit 1 and randomized to double-blind treatment at Visit 2. Participants will be randomized to LY3372689 low dose, LY3372689 high dose, or Placebo in a 1:1:1 ratio.

Participants will remain blinded to the original treatment arms while participating in the post-treatment safety follow-up period.

6.4. Study Intervention Compliance

Participant compliance with study medication will be assessed at each visit by direct questioning and/or counting returned tablets. The participant should be instructed to retain all empty drug packages after using up the medication in the package and to bring the empty packages and any unused medication to the clinic at each visit so that the clinic staff can record the amount of medication used since the last visit.

Compliance for the double-blind study periods will be assessed at telephone visits via questioning of the participant and/or study partner.

The administration of all study medication should be recorded in the appropriate sections of the eCRF.

Participants who consume 80-100% of the prescribed daily dose during this study will be considered compliant. A participant will be considered significantly noncompliant if he or she is judged by the investigator to have intentionally or repeatedly taken more or less than the prescribed amount of medication. Participants regarded as non-compliant may be discontinued at the investigator's discretion, in consultation with the Lilly-designated Medical Monitor.

6.5. Concomitant Therapy

Any medication or vaccine (including over-the-counter or prescription medicines, vitamins, and/or herbal supplements) that the participant is receiving at the time of enrollment or receives during the study must be recorded in the CRF, along with any changes to dose.

The Lilly-designated Medical Monitor should be contacted if there are any questions regarding concomitant or prior therapy.

Participants and their study partners will be instructed to consult the investigator or other appropriate study personnel at the site before initiation of any new medications or supplements and before changing dose of any current concomitant medications or supplements.

Use of benzodiazepines for treatment on an as-needed basis for insomnia or daily dosing as anxiolytics is permitted. Use of sedatives or hypnotics should be avoided for 8 h before administration of the cognitive and functional tests unless they are given chronically.

The following are prohibited concomitant medications during the study (refer to Manual of Operations for complete lists):

CCI

CCI

- Use of any investigational drug or device not specified in this study unless approved by the Lilly-designated medical monitor (topical may be permitted)
- Use of any drug of abuse, including but not limited to illicit amphetamine, cocaine, illicit opiates, propoxyphene, methadone, methaqualone, phencyclidine, and illicit barbiturate.
- Use of cannabis in a pattern of abuse.

6.5.1. Standard of Care for Alzheimer's Disease

To ensure standard of care for AD, use of approved prescription treatments for AD is permitted (but not a requirement) in this study. The section below provides additional guidance on managing concomitant medication use.

Double-Blind Period (Period 2a and 2b)

Use of approved or standard-of-care treatments for AD is permitted (but not a requirement) during the study, provided that the dose has been unchanged for 1 month before Visit 1. If approved prescription AD medication is a disease-modifying therapy (e.g., anti-amyloid or anti-tau), then dose must be stable for at least 3 months prior to V2. Doses of these medications should remain constant when possible, throughout the double-blind period (Visit 2 to 29). Any initiation or changes to standard-of-care medications should be done in consultation with the sponsor prior to implementing to determine if the participant would be allowed to continue in the study.

Nonmedication treatments for AD such as behavioral management are permitted but are subject to the same restrictions as medication treatment taken for AD.

Post-treatment Safety Follow-up Period (V802 and V803)

Use of approved or standard-of-care treatments including both symptomatic and disease-modifying therapies are permitted during the post-treatment safety follow-up period. Any changes to concomitant medication should be documented. Any concomitant medication used should be approved and used per the direction of the prescribing information.

6.6. Dose Modification

Dose modification of IP will be permitted for notable treatment-emergent AEs and AEs of special interest as determined by the study sponsor medical team, or as determined by the unblinded external DMC recommendations. Sponsor, site staff, and study participant will remain blinded to treatment assignments in all cases. A one-time dose reduction can be applied in a blinded fashion after sponsor safety review and/or an external DMC review (blinded or unblinded) on a case-by-case basis. Individual case dose reductions will result in individual participant reductions from 3.0 to 1.5 mg, or 0.75 mg to placebo, depending on the blinded treatment arm assignment of the participant. No change will be made for participants assigned to the placebo arm. If safety concerns remain for individual participants after dose reduction, a permanent discontinuation of study drug may be necessary. Based on a scheduled or ad-hoc safety review, the external DMC may also opt to trigger a dose reduction for the entire high-dose arm from 3.0 mg to a pre-established reduction dose of 1.5 mg for those participants assigned to the high-dose arm. There are no pre-established dose reductions for the low-dose arm. Study

team, participants, and blinded site staff will remain blinded to study dose and treatment arm in the event of dose reductions. In addition, treatment can be temporarily discontinued as an alternative to a dose reduction (see Section [7.1.1](#)).

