To explore the relationship between blood-based biomarkers and imaging	Blood-based biomarkers of AD pathology and neurodegeneration Imaging 
 • Flortaucipir PET • MRI
To assess the efficacy of LY3372689 to prolong time to clinical progression	CDR global score

Abbreviations: ADAS-Cog₁₃ = Alzheimer's Disease Assessment Scale – Cognitive subscale; ADCS-iADL = Alzheimer's Disease Cooperative Study – instrumental Activities of Daily Living; AD = Alzheimer's disease; AE = Adverse Event; CDR-SB = Clinical Dementia Rating Scale- Sum of Boxes; C-SSRS = Columbia-Suicide Severity Rating Scale; iADRS = integrated Alzheimer's Disease Rating Scale; ECG = electrocardiograms; MMSE = Mini Mental State Examination; MRI – Magnetic Resonance Imaging; PET = Positron emission tomography; PK = Pharmacokinetics.

- a Based on common close design, participants final endpoint time will be between 76-124 weeks.
- b Moderate tau pathology is defined as those who meet tau PET inclusion criteria for evidence of tau pathology consistent with Alzheimer's disease (Fleisher et al. 2020), but do not have widespread and high levels of cortical tau pathology.
- c High levels of cortical tau pathology by flortaucipir PET is defined by the top quartile of quantitative standardized uptake value ratios in a population of amyloid positive Alzheimer's participants and cognitively normal older controls (Pontecorvo et al. 2019).

Primary Estimand

The primary estimand is the overall treatment effect of LY3372689 versus placebo as measured by percent slowing of disease using the integrated Alzheimer's Disease Rating Scale (iADRS), in all participants with early symptomatic Alzheimer's disease (AD) and moderate cortical tau pathology burden while remaining on treatment up to 124 weeks after randomization. The 'initiation of approved prescription AD medication that is a disease-modifying therapy' and 'discontinuation of LY3372689' are considered as intercurrent events and are both addressed by the intention-to-treat (ITT) principle unless otherwise specified. An ITT analysis is an analysis of data by the groups to which subjects are assigned by random allocation, even if the subject does not take the assigned treatment, does not receive the correct treatment, or otherwise does not follow the protocol. No other intercurrent events are considered.

Secondary Estimand(s)

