4.10. Safety Analyses

All safety analyses will group subjects based on the actual treatment received. If a patient receives a treatment different than the randomized treatment for the duration of the placebo-controlled period, then that different treatment is the actual treatment; otherwise, the actual treatment is the planned treatment.

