4.10.1. Extent of Exposure

Days of exposure will be calculated for each participant:

$$\text{date of last dose} - \text{date of first dose} + 1.$$

Summary statistics will be provided for the total number of days and participant-years of exposure by treatment. Study drug treatment assignment will be listed.

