4.10.2. Adverse Events

Treatment-emergent adverse events (TEAEs) will be defined as events that occurred or worsened between the first dose (treatment start date) and two days post last dose (treatment end date), inclusive. Should there be insufficient data for AE start date, stop date, and time to make this

comparison, the AE will be considered treatment-emergent. The Medical Dictionary for Regulatory Activities (MedDRA) lower-level term (LLT) will be used in the treatment-emergent computation. The maximum severity for each LLT during the baseline period will be used as baseline.

An overview of AEs, including the number and percentage of participants who died, suffered serious adverse events (SAEs), discontinued due to AEs and who suffered TEAEs, will be provided. Comparison between treatments will be performed using Fisher's Exact Test.

Summaries of AEs by decreasing frequency of PT within SOC will be provided for the following:

- Pre-existing conditions
- TEAEs
- TEAEs by maximum severity
- TEAEs occurring in greater than or equal to 2% of participants by PT
- SAEs
- Adverse events reported as reason for study treatment discontinuation
- Adverse events of special interest (AESI) include, but not limited to, the following:

A black rectangular box containing the text 'CCI' in large, bold, red font.

These summaries will include number and percentages of participants with TEAEs. Treatment comparisons will be carried out using Fisher's Exact Test. A listing of AEs will be generated. Separated adverse events summaries will be provided for treatment period and follow-up period, respectively.

The following will be used to identify AESIs:

A black rectangular box containing the text 'CCI' in large, bold, red font.

The CCI logo is displayed in red text on a black rectangular background.

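### The SAP has no rule for individual dose reductions, so low-dose participants switched to placebo still accrue 0.75 mg exposure and are missed by the AE-discontinuation summary

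*Protocol*

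**What the plan says.** **Dosing rule.** Protocol 6.6 allows a one-time blinded reduction for an individual participant: "Individual case dose reductions will result in individual participant reductions from 3.0 to 1.5 mg, or 0.75 mg to placebo". For the third arm, "No change will be made for participants assigned to the placebo arm". Stopping is a further step: "If safety concerns remain for individual participants after dose reduction, a permanent discontinuation of study drug may be necessary". The same section lets the DMC lower the whole high-dose arm to 1.5 mg, and then adds: "There are no pre-established dose reductions for the low-dose arm". The regimen table in Protocol 6.1 footnotes only the 3.0 mg arm for a possible reduction. Protocol 6.1 also lists placebo as an investigational product.

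**Safety grouping.** SAP 4.10 moves a participant to another treatment group only if the different treatment was received for the whole placebo-controlled period; "otherwise, the actual treatment is the planned treatment".

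**Exposure.** SAP 4.10.1 takes last dose minus first dose plus 1. "Summary statistics will be provided for the total number of days and participant-years of exposure by treatment".

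**AE summaries.** The list in SAP 4.10.2 includes "Adverse events reported as reason for study treatment discontinuation". It has no entry for AEs leading to dose reduction, and neither does the DMC safety package in SAP 4.13.1.

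**Estimand.** SAP 1.1 names two intercurrent events, one of them discontinuation of LY3372689, and puts both under the ITT principle; "No other intercurrent events are considered". SAP 4.1 names the second event as discontinuation of the study drug.

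**The concern.** One blinded decision has different consequences in the three arms. A high-dose participant stays on active drug at half the dose, a low-dose participant comes off LY3372689 altogether, and a placebo participant sees no change. All three keep taking tablets, so none has discontinued study treatment.

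The SAP's default rules do not distinguish these cases. The low-dose switcher stays in the 0.75 mg group, later placebo tablets extend the last-dose date, and the adverse event that ended LY3372689 does not appear as a reason for stopping treatment. No planned summary shows that the switch took place. The DMC can itself recommend reductions, yet its package does not show those already made.

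At stake are two descriptions of low-dose tolerability: how long participants took 0.75 mg, and how often an adverse event ended active drug. The high-dose arm has a milder version of the exposure problem, since 1.5 mg days are counted as 3.0 mg. This would affect the whole arm if the DMC reduced it.

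**Working it through.** The documents state no figure for this point, so there is nothing to reproduce. The check applies the SAP's own rules to a switcher.

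**Inputs from the documents**
- 110 participants per arm (Protocol 1.1; 330/3 = 110).
- Double-blind treatment of 76 weeks, up to 124 weeks: 76 × 7 = 532 days and 124 × 7 = 868 days.
- Exposure, grouping and AE rules as above.

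**Assumed, because the documents are silent**
- 1 to 10 low-dose switchers.
- Switch at Week 12 (84 days), varied from Week 4 to Week 52.
- For arm totals, everyone takes tablets for 76 weeks.
- 5 low-dose discontinuations for an adverse event.

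**1. Exposure of one switcher**
- Tablets to Week 76: 532 days counted against 84 on 0.75 mg. Placebo share (532 − 84)/532 = 84%.
- Tablets to Week 124: 868 counted against 84. Placebo share 784/868 = 90%.
- Over switches at Weeks 4 to 52 and ends at Weeks 76 or 124, the placebo share runs from 32% (168/532) to 97% (840/868).

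**2. Exposure of the arm**

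Counted: 110 × 532/365.25 = 160.2 participant-years. On 0.75 mg with k switchers: [(110 − k) × 532 + k × 84]/365.25.

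| k | Participant-years on 0.75 mg | Overstatement |
|---|---|---|
| 1 | 159.0 | 0.8% |
| 3 | 156.5 | 2.4% |
| 5 | 154.1 | 4.0% |
| 10 | 148.0 | 8.3% |

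**3. AE discontinuation**

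As planned: 5/110 = 4.5%. Counting switches as stops of active drug, (5 + k)/110 = 5.5%, 7.3%, 9.1% and 13.6% for k = 1, 3, 5 and 10. Each switcher contributes 1/110 = 0.9 percentage points.

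**4. TEAE incidence**

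The triggering event stays in the low-dose arm. The TEAE window runs to two days after the last dose, so events on placebo tablets are added to that arm while the denominator is unchanged. If 40 of 110 participants (36.4%) had an event before any switch and 2 switchers had their first event afterwards, the table would show 42/110 = 38.2%. The count can only stay equal or rise.

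**5. Effect of converting low-dose switches alone**

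Take 4/110 AE discontinuations on placebo (assumed) and 5/110 on low dose. Fisher's exact p is 1.0. Adding 10 low-dose switches, and nothing for placebo participants given the same blinded decision, gives 15/110 against 4/110 and p = 0.014. A one-sided definition could create a difference by itself.

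**The case against.** A reader might infer that low-dose tolerability as a whole looks better than it is. The documents do not support that. AE, TEAE and SAE summaries are participant counts and percentages that include the triggering event, and they charge later placebo-time events to the low dose. No exposure-adjusted rates are planned, so participant-years are not the denominator of any planned rate.

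A reader might also tie this to Protocol 4.3, which mentions a potentially better safety profile at the lower dose. That remark rests on nonclinical toxicology and uses no table from this trial.

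It is tempting to count every 0.75 mg-to-placebo switch as an AE discontinuation. Stopping study treatment is at present defined identically in every arm. Converting one arm's blinded decisions and not the others' would bias against the low dose. This objection stands and shapes the fix.

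The estimand mismatch changes no analysis. Both named events follow the ITT principle, whose definition already covers a participant not taking the assigned treatment. It is a wording matter.

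Finally, the SAP makes no explicit choice here. It does not say whether last dose means last tablet or last active dose, and treatment assignment will be listed. But placebo is an investigational product, so last tablet is the natural reading, and a listing does not replace a summary. Suspensions, up to 6 weeks in total under Protocol 7.1.1, inflate exposure under the same formula in every arm and are not specific to the low dose.

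**Conclusion.** The concern holds for two measures. Under the SAP's default rules, low-dose exposure includes placebo days, and the AE-discontinuation summary omits adverse events that ended LY3372689 through a reduction. Both errors favour the low dose. TEAE and SAE incidence is not understated, and the ITT efficacy analysis is unaffected.

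The size cannot be known from the documents. The 0.8% to 8.3% overstatement of participant-years assumes 1 to 10 switchers, a Week 12 switch and 76 weeks of tablets for all. The 0.9 percentage points per switcher needs only the 110 denominator. With no reductions, nothing changes.

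Two wording points go with this. The two intercurrent-event phrases in SAP 1.1 and 4.1 diverge in exactly this case: a switch to placebo fits the first literally but not the second, because tablets continue. In Protocol 6.6, the low-dose reduction to placebo and the later statement that the low-dose arm has none pre-established must be reconciled. The latter follows the DMC's arm-level rule and probably refers only to that level, but the text does not say so.

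**What to change.** - **SAP 4.10.1:** define last active dose. Report exposure by dose actually dispensed (3.0, 1.5, 0.75 and 0 mg) from IWRS records after unblinding, net of documented suspensions.
- **SAP 4.10.2 and 4.13.1:** tabulate AEs leading to a blinded dose reduction in all three arms, including placebo participants for whom a reduction was decided but nothing changed. Add a combined row for dose reduction or discontinuation due to an AE, defined identically in every arm. Keep the existing discontinuation summary. Show 0.75 mg-to-placebo as stopping LY3372689 only in a labelled sensitivity row.
- **SAP 1.1 and 4.1:** use one phrase for the discontinuation event and say whether a switch to placebo falls under it.
- **Protocol 6.6:** reconcile the two statements on low-dose reductions.

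No dosing rule and no ITT efficacy analysis changes. The cost is SAP wording and minor programming; low-dose figures may become slightly less favourable. If no reductions occurred, the table says so.
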